#### (2) Hb values at each evaluation time point in the treatment period

##### 1) Hb values at each evaluation time point in the treatment period

Hb value and change of Hb value from the first day of the treatment period at each evaluation time point of the treatment period should be obtained, and its descriptive statistics should be calculated. Before and after comparison will be conducted for changes of Hb values from the first day of the treatment period to each evaluation time using the paired t-test.

LSMean, standard error, and 2-sided 95% CI of mean Hb value should be calculated using the MMRM model (with compound symmetry [CS] for a covariance matrix within subject variance) similar to that used in “mean Hb values at Weeks 20 and 24 of the treatment period”.

Furthermore, LSMean, its standard errors, and 2-sided 95% CI of the change from the first day of the treatment period should be calculated at each evaluation time point of the treatment period with using the MMRM model.

The time course diagram should be prepared for mean Hb values at each evaluation time point in the treatment period. The 95% CI of the mean will be represented by an error bar. The time course diagram should be prepared for Hb values at each evaluation time point in the treatment period for each subject.

2) Analysis of previous ESA formulation by type

An analysis similar to “1) Treatment period Hb value at each evaluation time point in the treatment period” should be conducted by the type of previous ESA formulation (epoetin alfa or epoetin beta, darbepoetin alfa, epoetin beta pegol). Only Conversion, Conversion (Hb value  $\geq 11.0$  g/dL), and Conversion (Hb value  $< 11.0$  g/dL) cohorts will be analyzed. No time course diagram will be prepared for each subject.

3) Analysis of previous ESA formulation by type and dose

An analysis similar to “1) Treatment period Hb value at each evaluation time point in the treatment period” should be conducted for weekly dose (darbepoetin alfa, epoetin beta pegol:  $\geq 15$   $\mu\text{g}$  and  $< 15$   $\mu\text{g}$ , 2 categories) of previous ESA formulation by type (epoetin alfa or epoetin beta, darbepoetin alfa, epoetin beta pegol). The number of patients classified by dose was set to be almost equal. Only Conversion, Conversion (Hb value  $\geq 11.0$  g/dL), and Conversion (Hb value  $< 11.0$  g/dL) cohorts will be analyzed. No time course diagram will be prepared for each subject.

(3) Proportion of subjects with mean Hb value within the target range ( $\geq 11.0$  to  $< 13.0$  g/dL),  $< 11.0$  g/dL, and  $\geq 13.0$  g/dL at each evaluation time point in the treatment period

The number, proportion, and 95% CI (Clopper-Pearson [Exact] method) of subjects with Hb value within the target range (11.0 g/dL to  $< 13.0$  g/dL, within),  $< 11.0$  g/dL (below), and  $\geq 13.0$  g/dL (above) at each time point of the treatment period should be provided. The McNemar test shall be used to compare before and after achievement for each treatment category at the first day of the treatment period and evaluation time point.

The proportion of subjects in each Hb value category (within the target range [11.0 g/dL to  $< 13.0$  g/dL],  $< 11.0$  g/dL or  $\geq 13.0$  g/dL) at each evaluation time point of the treatment period should be provided as a stacked bar graph assuming that the number subjects at the evaluation time point is 100%. Stacked bar charts should be separately prepared.

(4) Number of days from the first day of the treatment period required to reach the target Hb value range ( $\geq 11.0$  g/dL to  $< 13.0$  g/dL)

Descriptive statistics should be calculated for number of days required from the first day to reach target Hb value range (11.0 g/dL to  $< 13.0$  g/dL) of the treatment period. The number of days should be calculated as the first evaluation date reached target Hb value range – first date of the treatment period

+ 1. If target Hb value range is not achieved, the final date of evaluations – first date of the treatment period + 1 will be assumed.

A Kaplan-Meier plot should be shown for days from the first day of the treatment period required to reach the target Hb value range.

No subjects with an Hb value of  $\geq 11.0$  g/dL on the first day of the treatment period will be included in the calculation.

Only the Conversion (Hb value  $< 11.0$  g/dL) cohort will be analyzed.

(5) Hb value increase rate

Descriptive statistics should be calculated for the Hb value increase rate (g/dL/week).

The Hb value increase rate should be analyzed by 2 methods defined in the “4.13 Hb value increase rate”.

Only the Conversion (Hb value  $< 11.0$  g/dL) cohort will be analyzed.

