##### (1) ESA formulations

If a subject has received maximum dosages of MT-6548 for  $\geq 2$  weeks and meets all criteria below, investigators/subinvestigators may administer ESA as rescue therapy to improve Hb levels if necessary in order to secure subject safety. ESA rescue therapy may also be administered without meeting the criteria below if deemed necessary by investigators/subinvestigators in order to secure subject safety, such as in cases of acute decreases in Hb. MT-6548 administration will be discontinued if implementing ESA rescue therapy. Study drug treatment may resume if Hb levels improve, as long as there is no concomitant use with ESA. Subjects who are not expected to resume study drug treatment will

be withdrawn from the study.

- ✓ Anaemia or anaemia symptoms (e.g., fatigue, weakness, shortness of breath, chest pain, confusion, dizziness) become aggravated compared to the first day of the treatment period to the point they are clinically problematic.
- ✓ Hb levels drop to <8.0 g/dL.

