## 12. Withdrawal criteria and procedures

### 12.1 Withdrawal criteria

Subjects will be withdrawn from the study if the following criteria are met:

- (1) If the subject expresses a desire to withdraw from the study.
- (2) If it is discovered that the subject is clearly ineligible for study participation.
- (3) If investigators/subinvestigators determine that AEs make continued participation in the study difficult.
- (4) If investigators/subinvestigators determine that continuation of the study is inappropriate for a subject, such as if hyperviscosity syndrome occurs or if control of Hb within the target range is impossible.
- (5) If continuous haemodialysis is initiated, or if the subject receives a renal transplant.
- (6) If renal function recovers such that peritoneal dialysis is discontinued.
- (7) If pregnancy of the subject is discovered.
- (8) If the investigator/subinvestigator determines a subject should withdraw from the study for any other reason.

Rationale

- (1) Set out of ethical considerations.
- (2) (5) (6) Set in order to prevent study drug administration to subjects unsuitable for inclusion in safety or efficacy evaluation.
- (3) (4) (7) Set out of safety considerations.
- (8) Set in order to allow the investigator/subinvestigator to make determinations regarding study continuation for significant safety-related reasons other than those enumerated above.

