### 2.3 Rationale for sample size

Forty subjects will be enrolled in the treatment period

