#### [Rationale]

If the standard deviation of the mean Hb value, which is one of the efficacy endpoints of this study, is assumed to be 1.78 based on the upper limit of the two-sided 80% confidence interval in the MT-6548 300 mg group at the end of the primary efficacy evaluation period (Week 6) in a dose-finding study in Japanese patients with anemia associated with NDD-CKD (Study CI-0021), a sample size of 40 subjects allows value estimation with an accuracy of mean  $\pm 0.57$  g/dL (95% confidential interval [CI]). “Guidelines for the Treatment of Renal Anemia in Patients with Chronic Kidney Disease (JSDT 2015)” shows that Hb values vary in a range of about 1 g/dL in normal clinical contexts, which seems to indicate that the evaluation with the clinical significance is possible by estimating mean Hb values with an accuracy of mean value  $\pm 0.57$  g/dL (95% CI). A sample size of 40 subjects should also enable analysis of safety.

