## 8. Statistical Method

### 8.1 Basic matters

#### 8.1.1 Level of significance and confidence coefficient

When implementing tests, level of significance should be set at 2-sided 5%. Confidence interval (CI) will be 2-sided with a confidence coefficient of 95%.

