## 8.5 Efficacy analysis

As a general rule, efficacy analysis will be performed on the FAS. When necessary, descriptive statistics for continuous variables should be calculated and frequency and proportion will be calculated for discrete variables. Unless otherwise specified, a similar analysis should be conducted for each patient cohort. No data from the day after the rescue therapy implementation date should be included in the efficacy analysis.

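### The paired t-test of Hb change for primary endpoint 2 uses only subjects still observed after post-rescue data are dropped, so it leans upward if subjects leave mainly because Hb falls

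*SAP*

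**What the plan says.** Hb at each timepoint is the second primary endpoint (Protocol 5.3.1; SAP 3.1.1). For it, SAP 8.5.1(2) specifies:

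- a before-after comparison of "changes of Hb values from the first day of the treatment period to each evaluation time using the paired t-test";
- MMRM LSMeans, standard errors and 95% CIs, both of Hb and of its change, with no p-value requested. The covariance for the Hb model is fixed at compound symmetry;
- a figure of observed means: "The time course diagram should be prepared for mean Hb values at each evaluation time point in the treatment period".

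SAP 8.1.1 says that for tests the "level of significance should be set at 2-sided 5" per cent.

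These rules decide who has a usable value:

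- SAP 8.5: "No data from the day after the rescue therapy implementation date should be included in the efficacy analysis". SAP 7.3 says the same.
- SAP 7.2 does not allow a visit to be filled with a value from outside its window.
- Protocol 8.5.3(1) lists, among the ESA rescue criteria, that "Hb levels drop to <8.0 g/dL". Rescued subjects not expected to restart study drug are withdrawn.
- Protocol 12.1(4) lets the investigator withdraw a subject "if control of Hb within the target range is impossible".

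Protocol 13.3.2 planned only descriptive statistics and MMRM for this endpoint. The SAP added the paired t-test, and SAP section 9, including its erratum, does not list it as a change.

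**The concern.** A paired t-test at a visit includes only subjects with a value at that visit. Here the outcome itself can decide who is missing: a falling Hb can lead to rescue or withdrawal, and later values are then not used or not collected. The test therefore asks whether Hb changed among subjects who needed neither, while the stated analysis population is the FAS. The observed-mean figure has the same selection.

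The MMRM in the same subsection keeps each subject's values up to rescue. The p-value and the LSMean printed beside it can therefore describe different groups. A reader judging whether Hb was held or raised after the switch from ESA would be looking at a p-value and a plot that may both lean in the favourable direction.

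**Working it through.** **The plan's own figure.** The SAP has "Forty subjects will be enrolled in the treatment period", and the SD "is assumed to be 1.78 based on the upper limit of the two-sided 80% confidence interval in the MT-6548 300 mg group". Half-width of the 95% CI: t(0.975, 39) × 1.78/√40 = 2.023 × 0.2814 = 0.57 g/dL. This reproduces the stated precision.

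**Direction.** Let p be the proportion without a usable value. The FAS mean change is (1 − p) × (mean change in observed) + p × (mean change in removed), so

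bias of the observed mean = p × (mean change in observed − mean change in removed).

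The bias is upward only if the removed subjects would have had lower changes. The documents give neither p nor the gap.

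**Size, base model.** From the documents: n = 40, two-sided 5% (2.5% nominal for a false increase), SD 1.78, Hb <8.0 g/dL, and the visit schedule. Assumed:

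- Day 1 Hb within 9.0-12.5 g/dL (the conversion cohort's screening range), mean 10.5 or 11.0, SD 0.8, with the SD rising to its target by Week 6;
- 4-week correlation 0.8 or 0.9;
- no true change (tests centred on the true change);
- all Hb dropped after the first value below 8.0 from Week 8 onward.

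Week 24 results at SD 1.78:

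| Mean Hb | Correlation | Missing | Bias (g/dL) | False increases | Two-sided rejection |
|---|---|---|---|---|---|
| 10.5 | 0.8 | 17.2% | +0.242 | 12.9% | 13.1% |
| 10.5 | 0.9 | 13.0% | +0.218 | 13.8% | 14.0% |
| 11.0 | 0.8 | 11.5% | +0.163 | 7.8% | 8.3% |
| 11.0 | 0.9 | 9.2% | +0.158 | 8.8% | 9.4% |

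The formula shows what drives this: 0.242/0.172 = 1.4 and 0.158/0.092 = 1.7, so removed subjects would have changed by about 1.4-1.7 g/dL less than those kept. Against the planned precision, 0.158/0.57 = 28% and 0.242/0.57 = 42%. Independent reruns gave +0.15 to +0.24 and 8-14% false increases.

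**Sensitivity**

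| Change to the assumptions | Result |
|---|---|
| SD 1.5 | bias +0.07 to +0.13; false increases about 5-8% |
| SD 1.2 | bias at most +0.044; false increases 3.0-4.3% |
| SD 1.78, 50% chance of rescue per visit below 8.0 | two-sided rejection 6.4-9.8% |
| SD 1.78, 25% chance of rescue per visit below 8.0 | two-sided rejection 5.4-7.5% |
| SD 1.78, 50% rescue below 8.0 and 50% phlebotomy above 14.0 | bias +0.01 to +0.09 |
| Individual slopes (SD 0.8-1.6 g/dL by Week 24), rescue below 8.0 | 0.4-5.9% rescued; false increases 2.7-8.9% |
| The same, plus removal above 13.5 | false increases 1.4-4.4%; bias −0.07 to +0.07 |
| Stationary Hb, rescue below 8.0-9.0 | false increases 1.6-3.0%; bias zero or slightly negative |

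**Model-based alternatives on the same kind of data**

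- Likelihood estimate without a restrictive covariance: bias within 0.002 g/dL in the base model, with two-sided rejection of 4.5-6.8% (600 trials per scenario). With individual slopes, bias is within about 0.01.
- Compound symmetry: bias +0.01 to +0.05 in the base model. With individual slopes and triggers of 8.0-9.0, bias is +0.07 to +0.12 against +0.09 to +0.18 for the paired test. In those runs (400 trials each) it declared a false increase in 18-25%, more often than the paired test.

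**The case against.** **The size is not in the documents.** This stands. A reader might infer that the plan raises false increases to 8-14%. That range needs the SD of 1.78, which is a cautious planning value: an upper 80% confidence limit from Week 6 of a non-dialysis study. It also needs rescue at every first Hb below 8.0. Protocol 8.5.3(1) normally asks in addition for at least 2 weeks on maximum dosage and clinically problematic aggravation of anaemia or symptoms. Even then ESA is optional, although the investigator may also rescue outside those criteria. Dose titration was not modelled.

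**Upward bias is not inevitable.** This stands. Phlebotomy is also rescue therapy (Protocol 8.5.3(3)) and removes later values from high-Hb subjects.

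**It is not the only test of Hb change in the SAP.** This stands. SAP 8.5.2(1) has a second paired t-test, in the Conversion (Hb <11.0) cohort, and SAP 8.5.1(3) applies McNemar tests to Hb categories. The paired t-test is the only named test of change for primary endpoint 2.

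**The remedy is already printed.** This stands in part. The MMRM CI of change allows a reading against zero, but under compound symmetry that reading is not dependable when subjects drift apart over time.

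**LOCF covers it.** This stands only in part. SAP 7.4 derives a Week 24 LOCF value but does not assign it to this test, and it does not help earlier visits. Its performance depends on the model: bias is 0.00 to +0.03 with individual slopes, but −0.09 to −0.25 in the base model at SD 1.78.

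**Nothing is decided on this p-value, and selection would be visible.** This stands. The sample size rests on CI precision, no success criterion is stated, and the SAP reports numbers of subjects, rescue by period, discontinuation reasons and low Hb values. It limits the consequence without making the test describe the FAS.

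**Conclusion.** The concern holds in a conditional form. For primary endpoint 2, the only named significance test of change runs on subjects left after post-rescue values are dropped. If they leave mainly because Hb falls, the test and the observed-mean plot lean upward relative to the FAS.

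Under the base model the range runs from about +0.24 g/dL and 14% false increases (SD 1.78) to nearly nominal (SD 1.2). Softer rescue or phlebotomy can bring the bias to zero or below. The rescue rule, Day 1 spread and correlations are all assumptions.

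A reader might also infer that the trial's conclusion is at risk. The documents do not support that: the study is uncontrolled, its first primary endpoint is analysed by MMRM, and no decision depends on this test. The point is an inexpensive improvement to a supportive p-value and a figure.

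**What to change.** In SAP 8.5.1(2):

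1. Base inference on change from Day 1 at each visit on the MMRM LSMean of change (null hypothesis: change = 0, Kenward-Roger). Use the unstructured-first covariance sequence of 8.5.1(1) in place of fixed compound symmetry, and align 8.5.4.1, which also names compound symmetry.
2. Plot LSMeans with 95% CIs in the mean-Hb time-course figure, as 8.5.2(9) does for change in the iron indices.
3. Keep observed means, and the paired t-test if it is retained, as descriptive results labelled observed-case, with n at each visit.
4. Apply the same to the paired t-test in 8.5.2(1), and state whether it uses observed or LOCF values.
5. Record the change from Protocol 13.3.2 with its reason, as Protocol 13.4 requires. If the data are locked, report the result as a labelled added analysis.

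The cost is SAP wording and a little extra model output, with no new data and no work for sites. The test would rest on the missing-at-random assumption that the primary MMRM already makes, and p-values may be less favourable. Nine post-baseline visits give 9 × 10/2 = 45 covariance parameters with 40 subjects, so the fallback sequence may be needed. The report should state which structure was used, because ending at compound symmetry would correct the bias only in part.

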### 3. Endpoints

#### 3.1 Efficacy endpoints

##### 3.1.1 Primary endpoint

- (1) Mean Hb values at Weeks 20 and 24 of the treatment period
- (2) Hb value at each timepoint in the treatment period
- (3) Proportion of subjects with mean Hb values within the target range (11.0–13.0 g/dL), <11.0 g/dL, and  $\geq$ 13.0 g/dL at each time point in the treatment period

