### 8.5.1 Analysis of primary endpoint

#### (1) Mean Hb values at Weeks 20 and 24 of the treatment period

Descriptive statistics should be calculated for the primary efficacy endpoint of the mean Hb value at Weeks 20 and Week 24 of the treatment period. The average Hb value at each evaluation time was modeled using MMRM based on the following model, and the average Hb value for Weeks 20 and 24 of the treatment period should be obtained, and the least squares mean (LSMean), its standard error, and 2-sided 95% CIs for the mean Hb values should be calculated., No analysis will be performed for each patient cohort.

[MMRM Model]

- Covariate: response variable value of the first day of the treatment period
- Fixed effects: evaluation period,
- Degrees of freedom adjustment: Kenward-Roger method
- Covariance matrix within subject for each subject: unstructured (type = UN; unstructured)

When it was not converged using unstructured as a covariance matrix within subject variance, the setting of the covariance matrix within subject variance will be changed in the following order, and the analysis will be carried out using the covariance matrix within subject variance converged first.

Heterogeneous Toeplitz (TOEPH) → Heterogeneous AR (1) (ARH [1]) → Heterogeneous CS (CSH) → Toeplitz (TOEP) → First-order autoregressive (AR [1]) → Compound symmetry (CS)

- Random effects: subjects

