LSMean, its standard errors, and 2-sided 95% CI should be calculated for the change in iron-related measures (serum iron, TIBC, TSAT, and serum ferritin values) and hepcidin from the first day of the treatment period to each evaluation time point using the MMRM model (with compound symmetry [CS] for a covariance matrix within subject variance). Only the serum ferritin value at each evaluation time point of the treatment period should be analyzed similarly.

The time course diagram of changes in the iron-related measures (serum iron, TIBC, TSAT, and serum ferritin levels) and hepcidin from the first day of the treatment period to each evaluation time point should be prepared. The 95% CI of LSMean will be represented by an error bar. For only the serum ferritin value, a time course diagram should also be prepared for mean ferritin value at each evaluation time point of the treatment period. The 95% CI of the mean will be represented by an error bar.

The serum ferritin values should be shown as follows.

- ✓ The following scatter plot chart should be provided by treatment group. Linear regression should be performed to calculate the p-value and correlation coefficient of the test with zero slope as the null hypothesis.

x: Serum ferritin value at baseline

y: Serum ferritin value at Week 24 of the treatment period

- (10) Changes in hematocrit, red blood cell count, reticulocyte (number and rate), mean corpuscular volume, mean corpuscular hemoglobin, and EPO from the first day of the treatment period

Descriptive statistics of hematocrit, red blood cell count, reticulocyte (number and rate), mean corpuscular volume, mean corpuscular hemoglobin, and EPO should be calculated at each evaluation time point. In addition, the change from the first day of the treatment period should be obtained, and the descriptive statistics should be calculated. A paired t-test should be performed for before and after comparison of changes from the first day of the treatment period.

LSMean, its standard errors, and 2-sided 95% CI should be calculated for the change in hematocrit, red blood cell count, reticulocyte (number and rate), mean corpuscular volume, mean corpuscular hemoglobin, and EPO (MT-6548 group only) from the first day of the treatment period to each evaluation time point using the MMRM model (with compound symmetry [CS] for a covariance matrix within subject variance).

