#### **8.5.4 Statistical issues**

##### **8.5.4.1 Adjustment for covariates**

In the analysis of efficacy, in order to consider the effect of the measurement value of the first day of the treatment period on the change of each measurement, the analysis using the MMRM model (with compound symmetry [CS] for a covariance matrix within subject variance) should be conducted using the measurement value of the first day of the treatment period as a covariate in the general analysis including the analysis of the primary endpoint.

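### Compound symmetry fixed for by-visit Hb forces one variance on all visits and leaves the model-based 95% CIs miscalibrated: probably too wide early and, unless titration narrows late Hb spread, too narrow at Weeks 20 and 24

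*SAP*

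**What the plan says.** SAP 3.1.1 lists among the primary endpoints "2) Hb value at each timepoint in the treatment period". For it, SAP 8.5.1 (2) 1) states: "LSMean, standard error, and 2-sided 95% CI of mean Hb value should be calculated using the MMRM model (with compound symmetry [CS" (the bracket continues to name the within-subject covariance matrix). It calls this model similar to the one for the mean of Weeks 20 and 24. No fallback structure, robust standard error or reason for the different matrix is given.

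The model it refers to, in SAP 8.5.1 (1), reads "Covariance matrix within subject for each subject: unstructured (type = UN; unstructured". If that does not converge, six structures are tried in turn. The first three are the heterogeneous-variance ones (TOEPH, ARH(1), CSH), and the list ends "Toeplitz (TOEP) → First-order autoregressive (AR [1]) → Compound symmetry (CS". The same section sets "Covariate: response variable value of the first day of the treatment period" and "Degrees of freedom adjustment: Kenward-Roger method".

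In 8.5.1 (2) the compound-symmetry bracket is attached to the Hb level only. The sentence on change from the first day says just that the MMRM model is used. Compound symmetry for change comes from SAP 8.5.4.1 (Adjustment for covariates), which prescribes the MMRM "with compound symmetry [CS] for a covariance matrix within subject variance", with the first-day value as "covariate in the general analysis including the analysis of the primary endpoint". Read literally, that also contradicts the unstructured matrix in 8.5.1 (1).

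Descriptive statistics at each visit are planned as well. SAP 8.1.2 defines these to include the 95% CI of the mean.

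**The concern.** Compound symmetry assumes one variance for all visits and one correlation for all pairs of visits. With complete data every visit then gets the same standard error, set by the average variance. The fitted model adjusts for first-day Hb, so the variance that matters is what remains after that adjustment. At Week 2 most subjects are still near their starting value and little remains. By Weeks 20 and 24 the starting value predicts less and more remains. A pooled variance is then too large early and, unless overall Hb spread has shrunk, too small late. Kenward-Roger corrects for estimating the covariance parameters, not for a wrong structure.

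At stake is whether the model-based intervals for a listed primary endpoint cover at their nominal 95%, above all at the late visits where maintenance of Hb is judged. The SAP itself ranks compound symmetry last for the other primary Hb analysis.

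**Working it through.** **The plan's own precision figure.** Protocol 6.1 and SAP 2.3 give ±0.57 g/dL for SD 1.78 and 40 subjects. With the t quantile on 39 df, t × 1.78/√40 = 0.569, so the figure reproduces. It is one SD for one mean and says nothing about how variance moves across visits.

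**Inputs from the documents.** 40 subjects; nine post-baseline visits (Weeks 2, 4, 6, 8, 10, 12, 16, 20, 24); first-day Hb as covariate; two-sided 95% CI.

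**Inputs assumed, because the documents give none.** Complete data; correlation ρ per 2 weeks of 0.75, 0.85 or 0.90; raw SD moving linearly from 1 on the first day to f at Week 24. The SD scale cancels in the ratios.

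**Formulas.** The correlation between first day and week w is ρ^(w/2), so the baseline-adjusted variance is

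v_w = σ_w² × (1 − ρ^w), with σ_w = 1 + (f − 1) × w/24.

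With complete data the compound-symmetry variance is the mean of the nine v_w. The ratio of its half-width to the visit-specific one is about √(mean v / v_w), and coverage is about 2Φ(1.96 × ratio) − 1.

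**Worked case: ρ = 0.85, constant raw SD.** The v_w are 0.278, 0.478, 0.623, 0.728, 0.803, 0.858, 0.926, 0.961 and 0.980, with mean 0.737.
- Week 2: √(0.737/0.278) = 1.63, so 63% too wide.
- Week 20: √(0.737/0.961) = 0.876.
- Week 24: √(0.737/0.980) = 0.867, so 13% too narrow; coverage about 91%.

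**Range: Week 24 ratio (approximate coverage).**

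| Raw SD by Week 24 | ρ = 0.75 | ρ = 0.85 | ρ = 0.90 | Week 2 ratio |
|---|---|---|---|---|
| rises 20% | 0.855 (90.6%) | 0.804 (88.5%) | 0.762 (86.5%) | 1.52–1.98 |
| constant | 0.928 (93.1%) | 0.867 (91.1%) | 0.819 (89.2%) | 1.40–1.80 |
| falls 20% | 1.041 (95.9%) | 0.966 (94.2%) | 0.907 (92.5%) | 1.28–1.62 |
| falls 40% | 1.237 (98.5%) | 1.138 (97.4%) | 1.061 (96.2%) | 1.16–1.45 |

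**Simulation.** With one estimated baseline slope and t quantiles the picture is the same. At constant raw SD, Week 24 is 6 to 17% too narrow, with coverage about 89 to 93%. Across the scenarios the Week 2 half-width is 1.18 to 2.0 times the visit-specific one.

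**Second check, with the adjusted SD set directly** (6,000 runs per profile, correlation 0.7 per 4 weeks). Half-widths at Week 24 in g/dL, compound symmetry against visit-specific:
- adjusted SD rising 0.8 to 1.2: 0.315 against 0.379, coverage 90.1%
- equal at 1.0: 0.312 against 0.316, coverage 94.5%
- falling 1.2 to 0.8: 0.315 against 0.254, coverage 98.7%
- rising only because correlation with the first day fades (raw SD constant at 1): 0.272 against 0.313, coverage 91.4%, a gap of 0.041 g/dL

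Visit-specific variances gave 94.5 to 95.8% coverage at Weeks 20 and 24 in every profile. The equal-SD profile shows that decaying correlation between visits does no harm by itself; unequal adjusted variance does. If the adjusted SD really fell over time, the pattern would reverse: under the 1.2 to 0.8 profile, Week 2 coverage was 89.7%.

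**The case against.** **Titration may shrink late spread.** A reader might infer that the Week 20 and 24 intervals are simply too narrow. The documents do not support that. Neither gives a by-visit SD or says that Hb variance rises. Doses are adjusted toward 11.0–13.0 g/dL, data after rescue are dropped, and subjects whose Hb cannot be controlled may be withdrawn. All three can narrow the late distribution, and the table shows that a moderate fall in raw SD removes the late shortfall. This stands, so the late-visit direction is conditional.

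**The planning SD cannot be used as a Week 24 value.** Putting 1.78 at Week 24 against a small Week 2 SD would give a dramatic shortfall. But 1.78 is the upper limit of an 80% CI for an SD at Week 6 in one dose group of a non-dialysis study, and is not described as baseline-adjusted.

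**The practical weight is limited.** The descriptive CI at each visit uses that visit's own data, and the planned time-course plot shows the CI of the mean, not of the LSMean. No success criterion rests on the by-visit model CI. Nor do the two primary outputs contradict each other merely because their intervals differ: one is a two-visit average, the other single visits. All of this stands and limits the severity. It does not calibrate the model-based interval.

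**A simpler matrix may be deliberate.** The by-visit model is also run by cohort and by previous ESA type and dose, where an unstructured matrix may not fit. The model for the Weeks 20 and 24 mean is not run by cohort. That is a fair reason for economy in small cells. It is not a reason for compound symmetry in the FAS, nor for preferring it to a heterogeneous-variance structure.

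**Conclusion.** The point holds in this form: compound symmetry is fixed in advance for a listed primary endpoint, without a reason, although the SAP ranks it last for the same Hb series elsewhere. Because the model adjusts for first-day Hb, equal residual variance at all visits is unlikely, so the model-based by-visit CIs are likely miscalibrated.

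- Early visits: too wide in every scenario that lets correlation with first-day Hb fade, with a Week 2 half-width about 1.2 to 2.0 times the right one.
- Week 24: about 6 to 17% too narrow if raw SD is constant (coverage about 89 to 93%) and 14 to 24% too narrow if it rises 20%. Roughly right if it falls about 20%, and too wide if it falls 40%.

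These sizes rest on 40 subjects, complete data and assumed SDs and correlations; dropout was not modelled. That late intervals are too narrow is the more likely outcome if raw spread is stable, but it is not established. The concern is moderate, and the case for change does not depend on the direction, since visit-specific variances cover close to 95% whether variance rises, falls or stays flat.

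**What to change.** 1. In SAP 8.5.1 (2), for both Hb level and change in the FAS, replace compound symmetry with the unstructured matrix and fallback order of 8.5.1 (1). Name the structure for change explicitly.
2. In small cohorts and in the ESA-type and dose cells, use a heterogeneous-variance structure such as CSH where it converges.
3. Reconcile 8.5.1 (1), 8.5.1 (2) and 8.5.4.1 (Adjustment for covariates), so that one statement says which matrix applies to which Hb analysis.

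The cost is a few lines of SAP text and a changed covariance option in the same program. The price is more covariance parameters: for nine visits, 9 × 10/2 = 45 unstructured, 9 + 1 = 10 for CSH, and 2 for compound symmetry. Some small cells may not converge, and late-visit intervals may become wider.
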